9.5.2 Exhaled Breath Analytes, Puff Topography and Cartridge Weights

Descriptive statistics (number of observations, number of missing, mean, SD, median, minimum, maximum, the first quartile, the third quartile, 95% confidence interval, and coefficient of variation) will be provided for each analyte level (defined as the difference between the product sample value and the sham sample value), average puff duration, average flow rate, average puff volume, average number of puffs per cartridge, and for cartridge weight change by test product and use session (exhaled breath or ad libitum use). Separate linear mixed model for analysis of variance will be used to estimate effects of test product on the (1) each analyte level in the exhaled breath samples, (2) average puff duration, (3) average puff flow rate, (4) average puff

volume, (5) average puff number per cartridge, and (6) cartridge weight changes. The models will include sequence, study product, and period as fixed effects and subject nested within-sequence as a random effect. A frequency table will be used for the response to the Use the Product Again Questionnaire. Additional details of the statistical analysis will be provided in the statistical analysis plan.

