7.0 EVALUATION OF RESPONSE PARAMETERS**7.1 ANALYSIS OF PRIMARY RESPONSE ENDPOINTS**

Sham and test product-derived sample amount of each analyte as well as sham-corrected amount (SCA) of each analyte will be summarized, by test product, per Section 4.1. Sham-corrected analyte amounts will be computed by subtracting corresponding sham response values from test product response values.

Mixed effects ANCOVA models will be fit to separately to the following sham-corrected amount of 7 analytes that will be measured in exhaled breath repeatedly in each subject over the 4 days of Visit 2:

1. Nicotine
2. Glycerin
3. Propylene glycol
4. Menthol
5. Formaldehyde
6. Acetaldehyde
7. Acrolein

The Minimum Detection Limit (MDL) of each analyte is provided in Table 4.

Table 4. Limits of Detection for Exhaled Breath Analytes

Analyte	Nominal MDL (μg)
Propylene glycol	5
Vegetable glycerin	5
Nicotine	0.5
Menthol	0.5
Formaldehyde	0.2
Acetaldehyde	0.2
Acrolein	0.2

Statistical Analysis Plan

Analyte concentrations that are below the Minimum Detection Limit (MDL) will be set to the MDL value for analyses.

Two types of sampling containers were used for collection of the analytes from each subject's exhaled breath (Table 5). Sampling container 1 with one tube and one pad was used for capturing nicotine, glycerin, propylene glycol, and menthol while Sampling container 2 with one tube and 2 pads was used for capturing formaldehyde, acetaldehyde, and acrolein. Exhaled breath samples were collected in 2 independent sampling sessions, separated by 45 minutes, within each period (Figure 1B). Sampling container 1 was used to trap exhaled breath in the first sampling session, while sampling container 2 was used in the second sampling session.

There are two subsamples (1 tube + 1 pad) of each analyte, in each sampling container 1 and three subsamples (1 tube + 2 pads) of each analyte in sampling container 2. Enthalpy Analytical Company will provide data sets with the tube and pad analyte amount from each of the two types of Sample container, for each subject. Pad and tube MDL values of the same analyte will be different from one another. For each sampler, the final amounts for a given analyte will be computed in one of three ways:

1. When both the amounts of analyte in pad(s) and tube are above MDL, the exhaled breath sample (EBS) value will be the sum of the pad and tube values

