2. When the amounts of analyte in pad(s) and tube are both below MDL; EBS value will be the sum of the two MDL values. However, since the MDL is volume dependent, the sum will be considered as below MDL (i.e. <0.5).
3. When the amount of one analyte is MDL, but the other is above MDL. EBS will be the sum of the MDL value and the above BLLOQ value.

Descriptive statistics (number of observations, number of missing, mean, SD, median, minimum, maximum, the first quartile, the third quartile, 95% confidence interval, and coefficient of variation) will be tabulated for each of these analytes by test product. Frequency (n and %) of MDL values will be summarized for each product. If the percentage of MDL values for an analyte is more than 50% in any product group, the analyte will not be analyzed with a mixed model.

Statistical Analysis Plan

Each mixed model will be fit to the data by restricted maximum likelihoods. Covariance structures to account for dependencies among repeated measures, within subjects, will be selected for each model using AIC criteria.^[11] Four candidate covariance structures will be considered: compound symmetry, 1st order autoregressive, 1st order autoregressive with a random subject effect, and unstructured. Each model will include period-specific sham values (as a covariate), sequence, study product, and period as fixed effects; subjects nested within-sequence will be modeled as random effects. Standard residual analyses will be used to examine validity of assumptions for the fixed effect distributions. Response variables will be appropriately transformed (e.g., log, reciprocal, or square root) if the residuals indicate distributional assumptions don't hold. The models will be refit to the transformed data and residual analyses again be performed verify that the transformations corrected the problems.

Mean SCA response with (95% confidence limits), for each test product, will be estimated using SAS Least square means methods in each model. Estimates will be back-transformed to the original scale as necessary. Analyte LSmean estimates (with 95% CIs) for each test product will be tabulated for each model. As an example, the SAS Proc Mixed code to fit the Mixed effects ANCOVA model [with an AR(1) covariance structure] is provided below:

```
ods graphics on;
proc mixed data=evap_data method=REML;
  class seq test_product period subject;
  model Analyte = sham § seq period test_product/residual DDFM=KR;
  Random subject (seq); †

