  Repeated /type=AR(1) subject=subject(seq); ‡
  lsmeans test_product/cl alpha=0.05;
  ods output lsmeans=mndat;
  title1 'Fit a 4x4 crossover design mixed effects ANCOVA';
  title2 'with a baseline(sham) covariate adjustment'; run;
```

§ amount (µg) of exhaled analyte from sham is entered in the model as a “baseline” covariate
† explicit inclusion of the subject in a random statement will depend upon the selected covariance structure (Little et al. 2000).
‡ AR1 requires a Random subjects statement, but the UN structure does not.

Statistical Analysis Plan

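### The 95% interval for each product's mean sham-corrected amount treats the subtracted sham mean as known, so its coverage can fall below or rise above 95%

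*SAP*

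**What the plan says.** SAP 7.1 defines the response as a difference: "Sham-corrected analyte amounts will be computed by subtracting corresponding sham response values from test product response values". It models that difference: "Mixed effects ANCOVA models will be fit to separately to the following sham-corrected amount of 7 analytes". The same sham value is also a regressor: "Each model will include period-specific sham values (as a covariate), sequence, study product, and period as fixed effects". The estimate to be reported is stated as follows: "Mean SCA response with (95% confidence limits), for each test product, will be estimated using SAS Least square means methods in each model". The sample code requests "lsmeans test_product/cl alpha=0.05" with no AT option, so SAS holds the covariate at its observed mean. A code footnote describes sham as a baseline covariate.

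Protocol 9.5.2 has no such covariate: "The models will include sequence, study product, and period as fixed effects and subject nested within-sequence as a random effect". It leaves further detail to the SAP.

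The primary objective (Protocol 2.1, SAP 1.1.1) is the change between sham and product use for each product. SAP 7.1 also tabulates a descriptive 95% CI by product, and Protocol 9.5.2 defines the analyte level for that purpose as product minus sham. Neither document gives an SD for sham or product amounts.

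**The concern.** Adjusting for a baseline value is routine when the output is a contrast between treatments, because the covariate mean cancels. Here the stated output is each product's own mean change from sham, where it does not cancel. The sham mean is estimated from the same 32 subjects and is part of the quantity reported, yet LSMEANS conditions on it. The interval then has the right width only under particular relations between sham and product amounts, and the plan neither states nor checks which relation holds.

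These are the primary estimates, and they are meant to feed models of non-user exposure (Protocol 1.3). An interval with unknown coverage weakens that use.

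**Working it through.** **The plan's own figure.** SAP 1.5 states 8 replications per sequence: 32 / 4 = 8, which reproduces. There is no power or precision calculation to reproduce.

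**Algebra (untransformed SCA).** Let P be the product amount, S the sham amount and D = P − S. If D = Xb + βS + e, then P = Xb + (β + 1)S + e. Residuals and variance estimates are identical and the slopes differ by exactly 1. Hence

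LSmean(D at mean S) = LSmean(P at mean S) − mean S, with the same SE.

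The overall sham mean is subtracted as though it had no sampling error.

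**Size when the slope is the same between and within subjects.** The omitted variance is β² × [between-subject sham variance / 32 + within-subject sham variance / 128]. Assume product SD 1, sham SD r, a share ρ of sham variance between subjects, and product unrelated to sham (β = −1). The model variance of one product mean is 1/32, so

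model SE / true SD = 1 / √(1 + r²[ρ + (1 − ρ)/4]).

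For r = 1 and ρ = 0.5: omitted variance = 0.5/32 + 0.5/128 = 0.0195; model variance = 0.0313; ratio = √(1/1.625) = 0.784.

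**Simulation.** 1,500 trials per row, the four stated sequences, 32 subjects, complete data, REML with a random subject effect (compound symmetry), t on 28 df. Product SD apart from carried sham is 1, half of its variance between subjects. 'Carried' is the share of a subject's stable sham level that is also present in the product sample; day-to-day sham noise is never carried in these rows. Monte Carlo error near 95% is √(0.95 × 0.05 / 1500) = 0.6 points.

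| Sham SD / product SD | Sham variance between subjects | Carried | Model SE | True SD | Coverage, SAP model | Coverage, no covariate |
|---|---|---|---|---|---|---|
| 0.05 | half | none | 0.176 | 0.181 | 95.1% | 95.4% |
| 0.25 | half | none | 0.177 | 0.182 | 95.3% | 95.6% |
| 0.5 | half | none | 0.176 | 0.191 | 93.1% | 94.9% |
| 1 | none | none | 0.177 | 0.191 | 93.4% | 96.2% |
| 1 | half | none | 0.176 | 0.221 | 89.5% | 95.7% |
| 1 | 80% | none | 0.176 | 0.235 | 87.1% | 95.7% |
| 2 | half | none | 0.176 | 0.334 | 70.9% | 95.6% |
| 1 | half | half | 0.184 | 0.199 | 94.1% | 95.0% |
| 1 | half | all | 0.208 | 0.181 | 97.7% | 95.6% |
| 1 | 80% | all | 0.202 | 0.184 | 97.2% | 95.3% |

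The fifth row gives 0.176 / 0.221 = 0.80, against 0.784 from the formula.

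Further runs of the same kind, with 800 to 1,500 trials each:
- Nothing carried and 20–80% of sham variance between subjects: 86–92% at ratio 1, and 78–85% at ratio 1.5.
- Product rising one-for-one with sham, stable and daily parts alike: 95%.
- Stable background fully carried, daily noise not: 98.3–99.1% at ratio 1.5.

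**Why the interval can be too wide.** When stable background is in both samples, it cancels in D. The single fitted slope is pulled towards −1 by the daily sham noise (−0.87 in the ninth row). Adjusting with that slope puts subject background back into the between-subject variance, and the SE grows beyond the true SD.

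**The case against.** **Direction.** A reader might infer that the interval is always too narrow. The last two rows of the table show otherwise. The low-coverage figures need a background that appears in the sham but is absent from the product sample that follows it. Subtracting sham presupposes roughly the reverse. This objection stands, and the claim is therefore unreliable coverage, not systematic narrowness.

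**Materiality.** Values below the MDL are set to the MDL, which compresses sham variance when most shams are undetectable. An analyte with more than 50% MDL values in any product group gets no mixed model. Both rules limit the problem. Neither removes it for an analyte that is measurable in both sham and product samples. A reader might single out the aldehydes as the worst case, but the documents give no sham or product levels to support that.

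**Another interval exists.** The descriptive 95% CI in SAP 7.1, if computed on SCA as Protocol 9.5.2 defines it, includes the sham sampling error, and Protocol 9.1 justifies the sample size for description. That is fair. But the SAP names the model LS mean as its estimate of mean SCA, so two intervals for one quantity could differ with no rule for choosing between them.

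**Protocol conflict.** A reader might call the covariate a departure from the protocol. Protocol 9.5.2 defers detail to the SAP, so the addition alone is not a contradiction.

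**Response name.** The code calls the response `Analyte`. If that meant the raw product amount, the LS mean would not be SCA at all; the SE would be unchanged.

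**Conclusion.** The point holds for the per-product mean SCA and its 95% limits from the SAP 7.1 model. The SE leaves out the sampling error of the sham mean, and coverage depends on how sham relates to product amount:
- about 86–92% at equal SDs and 78–85% at a ratio of 1.5, if background does not carry over;
- near 95% if sham varies little, as when it sits near the MDL, or if product rises one-for-one with sham;
- about 97–99% if stable background carries over and daily noise does not.

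These figures rest on assumed SDs, complete data, untransformed SCA and compound symmetry. SAP 7.1 also allows transformations and three other covariance structures, which were not simulated. The defect and its mechanism are certain; its size in this trial is not. Product-versus-product differences are unaffected, because the common sham mean cancels. The change should be made, given that this is the primary estimate and the cost is small.

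**What to change.** For each product's mean SCA and 95% CI, remove `sham` from the MODEL statement and state in SAP 7.1 that the response is SCA. This restores the Protocol 9.5.2 model, whose coverage was 94.9–96.2% in the ten scenarios above and about 94–98% across all checks.

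If the covariate is kept for efficiency, take the interval from a bootstrap of subjects within sequence, recomputing the mean sham in each resample. The bootstrap's coverage was not simulated. With 8 subjects per sequence, plain resampling shrinks the variance by about 7/8 (SE by √(7/8) = 0.94), so specify a small-sample correction.

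Do not repair the SE by adding slope² × Var(mean sham). That works only when between- and within-subject slopes agree. With stable background carried over and daily noise not, it raised coverage to 98–99% at ratio 1 and 99.7–99.9% at ratio 1.5.

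Keep the sham-adjusted model with its default SE only for product differences, if any are reported.

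**Cost.** A wording change and a few lines of code. Some intervals will widen and others narrow. Dropping the covariate loses some efficiency when sham is unrelated to product amount: at equal SDs with half the sham variance between subjects, the true SD rises from 0.221 to 0.244, about 10%.

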3.0 ENDPOINTS AND COVARIATES

3.1 PRIMARY ENDPOINT

The primary endpoints for the study are each subject's sham-corrected amount of nicotine, glycerin, propylene glycol, menthol, formaldehyde, acetaldehyde and acrolein in exhaled breath from 10 puffs in each period for each of the 4 e-vapor products.

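### SAP 7.1 would, if residuals fail, transform a difference that can be zero or negative and back-transform to a figure that is not the mean sham-corrected amount

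*SAP*

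**What the plan says.** SAP 3.1 defines the primary endpoints as each subject's "sham-corrected amount of nicotine, glycerin, propylene glycol, menthol, formaldehyde, acetaldehyde and acrolein in exhaled breath from 10 puffs in each period". SAP 7.1 gives the computation: "Sham-corrected analyte amounts will be computed by subtracting corresponding sham response values from test product response values". The mixed models are fitted to that difference.

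Non-detects are substituted, in sham and product samples alike: "Analyte concentrations that are below the Minimum Detection Limit (MDL) will be set to the MDL value for analyses". Where pad and tube are both below the limit, the two limits are added, with this remark: "However, since the MDL is volume dependent, the sum will be considered as below MDL". A gate then removes mostly undetected analytes from modelling: "If the percentage of MDL values for an analyte is more than 50% in any product group", no mixed model is fitted.

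The default model is untransformed. If residuals fail, the rule is: "Response variables will be appropriately transformed (e.g., log, reciprocal, or square root) if the residuals indicate distributional assumptions" do not hold; the model is then refitted and the residuals are checked again. The reported quantity is described as follows: "Mean SCA response with (95% confidence limits), for each test product, will be estimated using SAS Least square means methods in each model". The next sentence adds: "Estimates will be back-transformed to the original scale as necessary". SAP 7.2 applies the same procedures to the modelled secondary endpoints.

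**The concern.** There are two separate difficulties.

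**Domain.** A signed difference is not a natural candidate for any of the three named transformations. The SAP gives no offset and no rule for zero or negative values. If software set those records to missing, they would be lost because of their own value, which the missing-at-random argument in SAP 4.2 does not cover.

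**Quantity estimated.** The primary objective (Protocol 2.1, SAP 1.1.1) is to estimate the change in total amount, and SAP 7.1 says that the model estimates mean SCA. A back-transformed LS mean estimates something else: a geometric mean (log), a harmonic mean (reciprocal) or a squared mean root (square root). Nothing in the SAP corrects or relabels it. This second difficulty needs no zeros and no non-detects.

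SAP 1.2 says that the data will be used to model exposure of non-users. With all values positive, each named transformation gives a figure below the mean whenever SCA varies, so that exposure would be understated if the model estimate were taken as the mean.

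**Working it through.** **Inputs from the documents.** 32 subjects in 4 sequences, hence 32/4 = 8 per sequence, as SAP 1.5 states. Nominal MDL 0.5 µg for nicotine and menthol, 5 µg for propylene glycol and glycerin, and 0.2 µg for the three aldehydes (SAP Table 4). **Not in the documents:** CV of SCA, sham level, sham-product correlation and detection rate. All values used for these below are assumptions.

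**Step 1: values that SCA can take.**
- Both samples below the same MDL: SCA = MDL − MDL = 0, for all seven analytes.
- Both below MDLs that differ because volumes differ: for nicotine with an assumed 5% to 20% difference, SCA = ±(0.5 × 0.05) to ±(0.5 × 0.20) = ±0.025 to ±0.1 µg.
- Product below MDL and sham at 1.2 × MDL: SCA = −0.2 × MDL, which is −0.1 µg for nicotine and −0.04 µg for an aldehyde.
- Both detected, with sham the larger: SCA is negative.

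**Step 2: the named transformations at those values.**

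| SCA | log | reciprocal | square root |
|---|---|---|---|
| 0 | undefined | undefined | 0 |
| below 0 | undefined | defined, but order reverses across zero | undefined |
| +0.025 to +0.1 µg | −3.7 to −2.3 | 40 to 10 | defined |

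Two nicotine non-detects could therefore give a reciprocal anywhere from ±10 to ±40, from volume differences alone.

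**Step 3: how often SCA could be negative.** For lognormal product and sham with median ratio r, common log-scale SD s = √ln(1+CV²) and correlation ρ, P(SCA ≤ 0) = Φ(−ln r / (s√(2(1−ρ)))).
- ρ = 0.5, CV 30% to 50%: 0.22 to 0.32 at r = 1.25; 0.01 to 0.07 at r = 2; about 0 at r = 5.
- CV 100%, r = 1.5/2/2.5/3: 31/20/14/9% at ρ = 0.5, but 14/3/1/0.2% at ρ = 0.9.

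The answer depends heavily on an unknown correlation. Analytes far above sham may have no negative values.

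**Step 4: back-transformed value over the mean, SCA all positive and lognormal.** Log: (1+CV²)^(−1/2). Square root: (1+CV²)^(−1/4). Reciprocal: (1+CV²)^(−1).

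| CV | 1+CV² | log | square root | reciprocal |
|---|---|---|---|---|
| 50% | 1.25 | 0.89 | 0.95 | 0.80 |
| 100% | 2.00 | 0.71 | 0.84 | 0.50 |
| 150% | 3.25 | 0.55 | 0.74 | 0.31 |

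**Step 5: only if zeros were dropped under log.** With zero fraction p, divide the log ratio by (1−p). At CV 50/100/150% this gives 1.19/0.94/0.74 for p = 0.25 (for example 0.894/0.75 = 1.19) and 1.79/1.41/1.11 for p = 0.50. The error could then go either way.

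**Step 6: what the 50% gate allows.** The SAP does not say whether sham samples count.
- Product samples only: 16 of 32 MDL values pass. At an underlying rate of 25% in all four products, P(more than 16 of 32) = 0.0006 per product and 1 − (1−0.0006)⁴ = 0.0024 for any of the four, treated as independent. At 50%, about 89% of trials would be barred, so the p = 0.50 figures are a boundary case.
- Sham samples also counted: if all sham samples are non-detects, the group is already at 32/64 = 50%. One product non-detect makes it 33/64 = 51.6% and bars the model.

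**The case against.** The rule is conditional on a residual check, and its list is introduced as examples of an appropriate transformation. One that is undefined for the observed data is arguably not appropriate. That stands: nobody is bound to use log, reciprocal or square root. It leaves the choice open until the data are seen, however, and it does not address the quantity estimated.

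The arithmetic answer is also delivered elsewhere. Protocol 9.5.2 requires the mean and 95% interval of product minus sham for each analyte by product, and SAP 7.1 tabulates descriptive statistics by product. Protocol 9.1 calls the purpose descriptive, and the example code requests no product contrasts. This stands too and limits the harm. It does not correct the model estimate, and two different figures could both be read as mean SCA.

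One can add that the objective does not say arithmetic mean, and that the SAP calls the tabulated items LS-mean estimates. The SAP's own sentence nevertheless names the quantity: "Mean SCA response with (95% confidence limits), for each test product, will be estimated using SAS Least square means methods in each model". Back-transformation follows directly, with no change of name.

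A reader might infer that the SAP discards records with SCA at or below zero. It does not say so; dropping is one possible consequence. A reader might also infer that half of a product's samples can be non-detects and still reach the model. That holds only if the gate counts product samples alone.

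**Conclusion.** The point holds as a conditional defect in the primary analysis. If the residual check fails and a named transformation is used, it may be undefined for some records. Even with all values positive, the back-transformed result would not be the mean SCA that the SAP says it estimates. The firm part is the algebra in steps 2 and 4. The size there (0.89/0.71/0.55 of the mean under log at CV 50/100/150%) rests on an assumed lognormal SCA. Steps 3 and 5 rest on further assumptions about correlation, zero fraction and dropping, and step 5 also on how the gate counts.

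The documents do not support the stronger conclusion that the primary results will be biased. Whether residuals will fail, how variable SCA is and how many values fall at or below zero are all unknown, and the untransformed mean will be available. The change should be made, but it does not undermine the study.

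**What to change.** In SAP 7.1, replace the transformation and back-transformation sentences for the primary endpoints, including the refit that goes with them, with:

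> SCA will be modelled untransformed and product LS mean SCA reported in micrograms. If residuals indicate skewness or unequal variance, 95% CIs for the LS means will use subject-level robust (sandwich) standard errors; a subject-level bootstrap within sequence may be added as a check. Any log-scale analysis will be secondary, will model the product amount (positive after MDL substitution) with log sham as covariate, and will be labelled a geometric mean product amount, not mean SCA.

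In SAP 7.2, which borrows the 7.1 procedures, state that any back-transformed estimate will be labelled by what it is, for example a geometric mean.

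**Cost.** A short text change, a little programming and possibly wider intervals. Coverage is only approximate at n = 32. In simulations of the 32-subject crossover under five assumed lognormal scenarios (compound symmetry, gate counting product samples only), the untransformed LS mean was 0.99 to 1.02 of the true mean. Coverage was 89% to 96% for the sandwich interval, 83% to 100% for the common-variance model interval and 90% to 95% for a studentized bootstrap. The bootstrap is no better overall than the simpler sandwich interval. The other covariance structures that SAP 7.1 allows were not simulated.
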